	
• Tolerability at the IMP injection site:
- Erythema/redness (diameter and graded severity)- Swelling/induration/edema (diameter and graded severity)- Pain assessment. 
Immunogenicity:
 
• Testing for ADA 
Pharmacokinetics:
 
• SAR156597 plasma concentrations 
Biomarkers:
 
• Measurement of protein biomarkers associated with the activity of the disease (COMP, CCL2) and the IL-4/IL-13 pathway (TARC, periostin, and eotaxin-3).• Archived blood samples for future assays of protein and mRNA biomarkers related to the disease and the response to therapy (requires separate informed consent).
ASSESSMENT SCHEDULE	
The study will comprise 8 on-site visits AND 4 phone calls:
 
• Visits:
- V1 (screening visit) between Day -28 and Day -1.- V2 (baseline visit) at Day 1 (first dosing).- Treatment period: V3 at Week 2, V4 at Week 4, V5 at Week 8, V6 at Week 12, V7 at Week 24.- V8 (End-of-Study [EOS] visit) at Week 35.- A time window of ± 2 days will be allowed for each visit.• Phone calls:
- For safety considerations phone calls will be made at Week 6, 16 and 20 during the treatment period, and at Week 30 during the follow-up period.

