	
*IMP administration given qw starting at V2 with the last dose given at Week 23.
 
STATISTICAL CONSIDERATIONS
 
Sample size determination:
 
Ninety-four (94) patients (47 patients per group) will yield 80% power to detect a difference versus placebo group of 3.6 in the mean change from baseline in mRSS at 24 weeks, assuming a standard deviation (SD) of 7 and using a 1-sided alpha of 5% (type I error).
 
The impact of treatment discontinuations in the context of an intent-to-treat (ITT) analysis where all mRSS data will be included in the analysis (regardless of adherence to treatment) was evaluated. Assuming that 10% of patients will discontinue the treatment, the estimated treatment effect at 24 weeks will be decreased from 4 (targeted treatment effect if all patients adhered to treatment) to 3.6 (targeted treatment effect in all randomized patients).
 
Analysis population:
 
The efficacy population will be the ITT population, which includes all randomized patients.
 
Patients in the ITT population will be analyzed according to the

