8.1.4 Route and method of administration

The route and method of administration are SC in the abdomen. SC injection sites should be alternated between the 4 quadrants of the abdomen (avoiding navel and waist areas) so that the same site is not injected for two consecutive weeks. The exact site of each injection will be documented on the source document. It is recommended that the injection occur at a site free of SSc involvement, if possible.

The IMP is administered every 7 days ± 2 days from initial IMP administration. This window is permitted per protocol to accommodate various circumstances (eg, pending laboratory results, management of AE, visit scheduling difficulty). The IMP administration should be performed by other site personnel, blinded from the person in charge of the preparation of the solutions and syringes.

If IMP administration is missed or temporarily discontinued, the initial schedule of injections may be resumed upon the investigator's medical judgment and discretion while the missed dose(s) will not be administered. This does not apply to permanent treatment discontinuation.

On days when the patient has a study visit, the IMP will be administered by the Investigator or delegate after clinic procedures and blood collection.

For doses not administered at the study site, the IMP will be administered by qualified site personnel and /or healthcare professionals (eg, visiting nurse service).

Patients should be monitored by site personnel/visiting nurse for at least 30 minutes or up to 2 hours as per country specific requirements after each administration for potential signs and symptoms that may suggest a hypersensitivity reaction.

For doses not given at the study site, a booklet will be provided to the patient to record information related to the injections; this booklet will be completed by the visiting nurse after each injection and will be kept as source data in the patient's study file. Patients will be instructed to bring the booklet back at the subsequent site visit for Investigator's review.

Between the protocol-scheduled on-site visits, interim visits to the site may be required for IMP dispensing. As an alternative to these visits, the IMP may be supplied from the site to the patient via a Sponsor-approved courier company where allowed by local regulations and approved by the patient.

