 - Patients will be monitored for at least 30 minutes or up to 2 hours as per country specific requirements after dosing for any signs or symptoms of a hypersensitivity reaction. An assessment of local tolerability at the injection site (present pain, erythema/redness, swelling/induration/edema and other related observations) will be conducted
- Provide treatment kits to be administered at Weeks 13, 14, 15, 16 and 17
- Schedule appointment for phone calls at Weeks 16 and 20 and for the End-of-Treatment (EOT) visit.

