2.1.5 Safety endpoints

The safety analysis will be based on the reported adverse events and other safety information, such as clinical laboratory data, vital signs, ECG.

Observation period

The observation period will be divided into 4 epochs:

- The **pre-treatment** epoch is defined as the time from the signed informed consent date up to the first administration of IMP.
- The **treatment** epoch is defined as the time from the first administration of the IMP to the last administration of the IMP + 7 days.
- The **residual treatment** epoch is defined as the time from the last administration of the IMP + 8 days to the last administration of the IMP + 84 days.

The treatment-emergent adverse event (TEAE) period will include both **treatment** and **residual treatment** epochs.

- The **post-treatment** epoch is defined as the period of time starting the day after the end of the TEAE period up to the end of the study (defined as last protocol-planned visit or last study assessment).

The on-study observation period is defined as the time from the first administration of IMP until the end of the study (defined as last protocol planned visit or last study assessment).

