2.4.3.2 Compliance

A given administration will be considered non-compliant if the patient did not take the planned dose of treatment as required by the protocol. No imputation will be made for patients with missing or incomplete data.

Overall percentage of compliance for a patient will be defined as $100 - (\% \text{ days with below-planned dosing} + \% \text{ days with above-planned dosing})$, considering that injections should be performed every week ± 2 days as per protocol.

Above-planned dosing percentage for a patient will be defined as $100 * \text{the number of days with more than 1 injection administration within the 5 days before divided by the duration of IMP injection exposure in days}$.

Below-planned dosing percentage for a patient will be defined as $100 * \text{the number of days with no injection administration within the previous 9 days divided by the duration of IMP injection exposure in days}$.

Treatment compliance, above-planned, and under-planned dosing percentages will be summarized descriptively as quantitative variables (number, mean, SD, median, minimum, and maximum). The percentage of patients whose compliance is $<80\%$ will be summarized. In addition, numbers and percentages of patients with $[0;5]$, $]5;10]$, $]10;20]$, and $>20\%$ of days with above or under-planned dosing will also be provided.

In addition, the following parameters will be summarized by treatment arm:

- The number of advanced injections (≤ 3 days apart from the previous injection, 4 days apart from the previous injection) and the number of delayed injections (more than 9 days between two consecutive injections).
- The number of patients with at least one advanced injection and the number of patients with at least one delayed injection. A patient could be counted in several categories.
- The frequency of IMP injections (mean (SD), median, Min:Max description) will be defined for each patient as the average number of days between two consecutive injections: $(\text{last injection date} - \text{first injection date}) / (\text{number of injections} - 1)$ for patients with at least 2 injections.

Cases of overdose are reported in the AE e-CRF pages as AESI if symptomatic or AE if asymptomatic. The reported cases of overdose will be described in the AE analysis (see [Section 2.1.5](#) and [Section 2.4.5.1](#)).

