2.4.4.1.3 On-treatment analysis

A secondary estimand will be the difference in mean change from baseline to 24 weeks in mRSS estimated during the on-treatment period (from the first administration of the IMP to the last administration of the IMP + 7 days). This estimand corresponds to a “while on treatment strategy”. This estimand will be considered for describing the effect of treatment as long as patients adhere to their randomized treatment.

As a secondary analysis, the change in mRSS from baseline to Week 24 will also be analyzed in the randomized and treated population using the same MMRM model as described above, including only post-baseline data measured during the on-treatment period (from the first administration of the IMP to the last administration of the IMP + 7 days), analyzed according to the treatment group allocated by randomization.

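### The on-treatment mRSS cut-off (last injection + 7 days) falls exactly on the Week 24 target day, so patients who took every dose can lose their Week 24 value through visit timing alone

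*SAP*

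**What the plan says.** SAP 2.4.4.1.3 sets out a secondary, while-on-treatment estimand for the change in mRSS to Week 24. It reuses the primary MMRM in randomized and treated patients, by randomized arm, with only post-baseline values "measured during the on-treatment period (from the first administration of the IMP to the last administration of the IMP + 7 days". Its purpose is given as follows: "This estimand will be considered for describing the effect of treatment as long as patients adhere to their randomized treatment". SAP 2.1.5 runs the residual-treatment epoch "from the last administration of the IMP + 8 days to the last administration of the IMP + 84 days", so day + 7 counts as on treatment and day + 8 does not.

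The schedule comes from these places:

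- **Last dose.** Protocol synopsis: weekly dosing from Visit 2, "with the last dose given at Week 23".
- **Dosing window.** Protocol 8.1.4: "The IMP is administered every 7 days ± 2 days from initial IMP administration".
- **Visit window.** Protocol synopsis: "A time window of ± 2 days will be allowed for each visit".
- **Compliance.** SAP 2.4.3.2 assesses it "considering that injections should be performed every week ± 2 days as per protocol".
- **Study days.** SAP 2.5.4, Table 3: the first injection is Day 1; the Week 24 target is Day 169, with an analysis window of Days 127 to 207.
- **Visits after Week 12.** Protocol 10.1.7: "Schedule appointment for phone calls at Weeks 16 and 20 and for the End-of-Treatment (EOT) visit". The flow chart (Protocol 1.2) has no mRSS between Weeks 12 and 24.

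SAP 2.4.4.1.7 and 2.5.2 use the same last injection + 7 days to define treatment discontinuation for imputation. The protocol's own restricted analysis (11.4.2.1) uses the TEAE period, which 11.4.3 ends 84 days after the last dose.

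**The concern.** One dosing interval after the last dose is a natural boundary, but here it lands on the day of the endpoint visit with no allowance for either window. A patient who takes every dose and keeps every window can be classed as off treatment at Week 24 because the visit was a day late or the last dose a day early. That conflicts with the stated aim of describing adherent patients.

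Nothing else in the SAP restores the value. The Day 127 to 207 window does not, because the on-treatment restriction is a separate filter. Only an unscheduled mRSS on or after Day 127 and by the cut-off could fill the gap. The patient's Week 4 to Week 12 values stay in the model, and Week 24 is treated as missing at random. Within the SAP this is the only primary-endpoint analysis restricted to treated time.

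**Working it through.** **Dates.** With Day 1 as first injection, as in SAP Table 3:

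- Week 24 target = 1 + 24 × 7 = Day 169, which reproduces Table 3.
- Scheduled Week 23 dose = 1 + 23 × 7 = Day 162.
- Cut-off = 162 + 7 = Day 169, so the margin is zero.

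**Which combinations lose the value.** Let L be the offset of the last dose and V the offset of the visit, each from −2 to +2 days. The value is lost when 169 + V > 162 + L + 7, that is, when V > L. This holds for 10 of the 25 pairs. For example, a dose on Day 162 with a visit on Day 170 loses the value, and so does a dose on Day 160 with a visit on Day 169.

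The permitted gap from last dose to visit runs from 167 − 164 = 3 days to 171 − 160 = 11 days. Pairs lost by cut-off are: + 7 days, 10; + 8, 6; + 9, 3; + 10, 1; + 11, 0.

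**Share of completers affected.** The documents give no timing data, so these are assumptions. If L and V are independent with the same distribution, the share is (1 − P(V = L))/2. Off-day probability is split equally over the other four days.

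| Assumption | Calculation | Share lost |
|---|---|---|
| Uniform over ± 2 days | (1 − 5 × 0.2²)/2 | 0.400 |
| 70% on the exact day | (1 − 0.7² − 4 × 0.075²)/2 | 0.244 |
| 90% on the exact day | (1 − 0.9² − 4 × 0.025²)/2 | 0.094 |
| 95% on the exact day | (1 − 0.95² − 4 × 0.0125²)/2 | 0.048 |

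If visits tend to run late (V = −2, −1, 0, 1, 2 with probabilities 0.05, 0.05, 0.5, 0.2, 0.2) and 70% of doses are on the day, the share is 0.075 × 0.95 + 0.075 × 0.90 + 0.70 × 0.40 + 0.075 × 0.20 = 0.434. If half of patients shift dose and visit together (V = L, never lost), the four tabulated shares halve to about 20%, 12%, 5% and 2%.

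**Precision.** The plan assumes 10% discontinuation, so completers per arm = 47 × 0.9 = 42.3. With a fraction m of Week 24 values lost and Week 12 to Week 24 correlation ρ, the standard error is multiplied by √(ρ² + (1 − ρ²)/(1 − m)). ρ = 0.7 is an assumption; ρ = 0 means no recovery from earlier visits.

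With the plan's SD of 7, the base SE is 7 × √(2/42.3) = 1.52. The 90% CI half-width, with t quantiles on 2n − 2 degrees of freedom, is 2.53 points.

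| Loss m | Week 24 values left per arm | SE factor, ρ = 0.7 | SE factor, ρ = 0 | 90% half-width |
|---|---|---|---|---|
| 0.40 | about 25 | 1.158 | 1.291 | 2.95 to 3.29 |
| 0.24 | about 32 | 1.078 | 1.147 | 2.74 to 2.92 |
| 0.09 | about 38 | 1.025 | 1.048 | not tabulated |
| 0.05 | about 40 | 1.013 | 1.026 | 2.57 to 2.60 |

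**Imputation.** The same rule matters in SAP 2.4.4.1.7 and 2.5.2 only if the imputations are triggered: more than 5 patients without a Week 24 mRSS (2.4.4.1.1), or more than 20% missing for % predicted FVC (2.4.4.4.8) or CRISS (2.4.4.4.10). Reading Week 24 as Day 169, an active completer with a missing Week 24 value and a last injection before Day 162 is imputed from the placebo model. Observed active values later than + 7 days are left out of the on-treatment imputation model, but they remain as observed values in the analysis.

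**The case against.** This is one secondary analysis. The primary treatment-policy analysis keeps every Week 24 value, and affected patients still contribute their earlier visits. Seven days is one dosing interval and is used consistently for the treatment epoch, exposure, time to discontinuation and imputation. The protocol's 84-day period is no better as an on-treatment definition, since it would keep values obtained long after stopping. All of this stands, and it limits how much weight the point carries.

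The size is also uncertain. The largest shares need wide, independent timing or a late-visit pattern. The trough PK sample at Visit 7 suggests that visit and last dose may be tied together, which pulls the share down. At 5% loss the effect is negligible. This too is fair, and it is why a range is given.

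A narrower objection is that SAP 2.4.3.2 judges compliance by the gap between injections, not by the offset from schedule. A Week 22 dose at + 2 days followed by a Week 23 dose at − 2 is only 3 days apart and counts as an advanced injection. So not every dosing history behind the 25 pairs is compliant in the SAP's sense. But every last-dose offset can be reached with accepted gaps. Two gaps of 6 days followed by gaps of 7 give − 2, and two gaps of 8 followed by gaps of 7 give + 2. The 10 losing pairs therefore remain possible for compliant patients.

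Finally, neither imputation section states which calendar day stands for Week 24 when the value is missing. Day 169 is the natural reading of Table 3, but it is a reading.

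**Conclusion.** The concern holds. The zero margin and the 10 of 25 losing combinations follow from the documents' own dates and windows and need no assumption. The share of completers affected does: about 2% to 43% under the patterns tried. The 90% half-width grows from about 2.5 mRSS points to about 2.6 at 5% loss, 2.7 to 2.9 at 24%, and 2.9 to 3.3 at 40%. If visit timing is unrelated to outcome, the harm is lost precision, and an analysis that no longer matches its stated purpose, rather than bias. It is worth correcting because the correction is cheap, not because the primary conclusion depends on it.

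**What to change.** In SAP 2.4.4.1.3, for this efficacy analysis, count the Week 24 visit of any patient who received the Week 23 dose as on-treatment if it falls within last injection + 11 days (7 + 2 for the dosing window + 2 for the visit window). Keep + 7 days for all other patients. State what receipt of the Week 23 dose means, for instance an injection on Days 160 to 164.

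Apply the same rule in 2.4.4.1.7 and 2.5.2, so that these patients are on treatment at Week 24 there too. Leave the safety epoch in 2.1.5 and the exposure definition in 2.4.3.1 unchanged.

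In the same edit, align Appendix B with 2.4.4.1.3. The appendix names the safety population, which is analysed as treated, whereas the section specifies randomized and treated patients by randomized arm.

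The cost is SAP wording and one derivation, plus a second, efficacy-specific on-treatment definition beside the safety epoch. Applying + 11 days to everyone would be simpler, but early discontinuers could then contribute values up to 11 − 7 = 4 days later than now. No dose, visit or data collection changes.

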2.4.4.1.4 Sensitivity to error in randomization strata

In order to assess the robustness of the primary analysis to randomization stratum mistakes (ie, the stratum recorded in IRT differs from the actual one), if more than 15% of patients have been randomized to the wrong stratum, the MMRM model will be re-run including the actual stratum as per the eCRF instead of the stratum recorded in IRT.

2.4.4.1.5 Sensitivity analysis on rater

In order to assess the impact of different raters evaluating a same patient from baseline, the MMRM model will be re-run using only mRSS values from all visits evaluated by the same rater as baseline. All other values evaluated by different rater from baseline will be considered missing at random in this sensitivity analysis.

2.4.4.1.6 Sensitivity analysis on high mRSS

The MMRM model will be re-run using only patients with mRSS score superior or equal to 15 at baseline.

2.4.4.1.7 Control-based pattern imputation

In addition to the MMRM method, the control-based pattern imputation method will be used to address missing values, in the randomized population, followed by the testing of treatment arms using an analysis of covariance (ANCOVA) model, with the intent to evaluate the robustness of the primary analysis using a different statistical method.

Imputation rules

The control-based pattern imputation assumes:

- After treatment discontinuation (defined for this analysis as last injection + 7 days), patients from the experimental treatment arm (no longer receiving the experimental treatment) will exhibit the same future evolution of the disease as patients on the control treatment (who are also not exposed to the experimental treatment). In this experimental arm, missing values before treatment discontinuation will be considered missing at random and will be imputed using a model estimated using only samples from the experimental arm collected before treatment discontinuation.
- Missing on-treatment mRSS values in the experimental arm will be imputed from other on-treatment measurements in the experimental arm assuming MAR, using SAS® MI procedure. Only mRSS values collected during the on-treatment period will be included in the imputation model. This way, missing mRSS values during the on-treatment period will be imputed based solely on observed on-treatment mRSS values. The imputation model will include the randomization strata (as per IRT, SSc-ILD: Yes/No), baseline mRSS value, and all time points (Week 4, Week 8, Week 12, Week 24). Since the pattern of missing data will be non-monotone, a Monte-Carlo Markov Chain (MCMC) method will be used. A minimum value of 0 and a maximum value of 51 will be specified in order to respect the range value for mRSS.
- Whatever the timing of treatment discontinuation, patients who discontinue from the control arm are assumed to evolve in the same way as control patients who remain in the study. Therefore, their missing values will be considered as missing at random and imputed using a model estimated using all samples collected from the control arm.

Imputation method

To account for the uncertainty, missing values will be imputed 100 times to generate 100 complete datasets, using the MI SAS procedure. The change from baseline at Week 24 will be then derived from observed and imputed mRSS at this time point.

The 100 complete datasets will be then analyzed using an ANCOVA model with treatment group and randomization strata (as per IRT, as defined in [Section 1.1](#)) as fixed effects, and the baseline mRSS value as continuous covariate, and change in mRSS from baseline to Week 24 as explained variable. The MIANALYZE SAS procedure will be used to generate valid statistical inferences by combining results from the 100 analyses using Rubin's formulae.

The number of imputations (100) will be informally verified by replicating sets of 100 imputations and checking whether the combined results are stable. If not stable, the number of imputations will be increased and informally checked as above, and thus until stable estimates are obtained.

Non continuous variables included in the imputer's model (ie, treatment group, randomization strata) are not expected to be missing.

Only imputed values during the on-treatment period will be kept in the final datasets that will be analyzed using ANCOVA. Imputed values during the post-treatment period will be discarded and replaced by imputed values described in the next paragraph.

Imputation programming

In order to implement the control-based pattern imputation, we will break the imputation process into a sequence of multiple calls to PROC MI, where each call is intended to impute missing values at one time-point only. The general logic of such a strategy is as follows.

1. With each call to PROC MI, impute only one time-point using a regression-based MI method for monotone missingness. Variables included in the regression model are randomization strata and mRSS values from previous time-points (including baseline).
2. When imputing missing values for time-point t , the input dataset should include all control patients, but only those patients from the experimental arm who have values at time-point t missing (only those who need imputation at time-point t). Since patients from the experimental arm with non-missing values at time-point t are not included in the input dataset, they will not contribute to the estimation of an imputation model for time-point t . The imputation model will then be estimated using control patients only, while this call to PROC MI will impute missing data at time-point t for all patients who need imputation at that time-point. This way, patients from experimental arm will be imputed based on the control patients' model. Note that treatment arm should not be included as an effect in this model.
3. Repeat (2.) for all other time-points sequentially. Patients whose missing values were imputed in the last call to PROC MI will be included in the input dataset for the next call to PROC MI except for patients in the experimental arm having non-missing data at time-point $t+1$ (patients with non monotone missingness). Thus data for time-point t , imputed during the last call, will be used as predictor variables in the next call to PROC MI (for time-point $t+1$) (6).

This imputation allows the patient to continue from the level achieved under the active treatment as though it had been achieved under the reference treatment. One consequence is that if a patient on active is above the reference mean then this positive residual will feed through into subsequent observations, to a degree determined by the correlation pattern in the referenced arm. Hence, the patient's profile will slowly decay back toward the mean for reference at later times (7).

The imputed mRSS data will be between 0 and 51 (range value for mRSS score).

